1. STUDY IDENTIFIERS

1.1. Title of study

An open-label, randomized, parallel-arm study investigating the efficacy and safety of intravenous administration of pamrevlumab versus standard of care in patients with COVID-19.

1.2. Clinical study number

FibroCov-01 / FGCL-3019-IST-014.

1.5. Type of study

Investigator Initiated Trial - Phase 2/3.

1.6. Study rationale

Recent data, including those from Italian hospitals, indicate the presence of interstitial pneumonia in a subset of patients infected with novel coronavirus SARS-CoV-2 requiring hospitalization. The interstitial pneumonia is usually bilateral and responsible for reduced efficiency of gas exchange, potentially leading to respiratory failure, intubation and finally death. Data on file, generated by FibroGen, suggest that CTGF (connective tissue growth factor; CCN2) may promote vascular leakage, and administration of pamrevlumab, an anti-CTGF monoclonal antibody, can reverse edema. This suggests that administration of pamrevlumab may improve gas exchange by attenuating edema associated with the virus-induced pneumonia.

In addition, published data in several animal models (Pi et al. 2018; Bickelhaupt et al. 2017; Sternlicht et al. 2018; Makino et al. 2017; Booth et al. 2010) indicate that pamrevlumab alters trafficking of certain immune-related cells. In a radiation-induced lung fibrosis (RILF) model, the mechanism by which a rapid reversal of pneumonitis occurs appears to be via pamrevlumab deactivation of myofibroblasts that decreases their secretion of chemokines (Sternlicht et al. 2018). This hypothesis remains to be confirmed for the RILF model, and the mechanism(s) by which pamrevlumab alters immune cell trafficking remains to be determined. It should also be noted that none of these models involved active viral infections, so it is unclear if pamrevlumab would broadly affect inflammation associated with SARS-Cov-2. However, if blocking CTGF attenuates inflammation, pamrevlumab might reduce symptoms associated with the virus-induced cytokine storm.

Finally, pathophysiology resulting from SARS-Cov-2 may lead to interstitial lung fibrosis in patients that survive the infection. CTGF is a key mediator of pro-fibrotic pathways and its inhibition might mitigate interstitial fibrosis in the post-acute infection setting. Data from a retrospective cohort study in Wuhan, China (Zhou et al. 2020) show that more than one third of COVID-19 patients surviving pneumonia have a residual respiratory failure, due to the presence of fibrotic changes in the lung. The well documented anti-fibrotic effects of pamrevlumab (Richeldi et al. 2019) might help in reducing the fibrotic residual damage in the lung of patients with COVID-19.

In addition to lung damage caused by the immune system's attempt to eradicate the viral infection, ventilation of ARDS patients may also contribute to development of pulmonary fibrosis (Cabrera-Benitez et al. 2014). In ARDS patients that developed fibrosis, there was a statistically significant correlation between ventilator mechanical power and the abundance of TGF β and CTGF in serum (Xie et al. 2019). CTGF has been shown to be elevated in ventilated preterm sheep, and to increase with gas volume (Wallace et al. 2009) and flow (Bach et al. 2008). CTGF expression also increases with tidal volume in neonatal rats (Wu et al. 2008). Together, these data suggest that CTGF may mediate some aspects of ventilator-induced lung damage. Hyperoxia may also contribute to acute lung injury in intubated ARDS patients (Schwarz et al. 2001). In the rat neonatal hyperoxia model of bronchopulmonary dysplasia, an antibody with activity similar to that of pamrevlumab was able to improve lung development in non-ventilated pups (Alapati et al. 2011). This suggests that pamrevlumab might attenuate some of the pathology associated with hyperoxia.

A Phase 2 dose-response study of pamrevlumab was performed in pancreatic cancer patients (Picozzi et al. 2017). In this study, pamrevlumab (FG-3019) was administered every two weeks at doses up to 45 mg/kg, or weekly at 22.5 mg/kg after a loading dose of 45 mg/kg. Patients that had trough plasma levels of pamrevlumab immediately before the second dose that was greater than 150 μ g/ml exhibited better overall survival than those whose plasma trough levels were less than 150 μ g/ml. Patients that had ascites exhibited lower plasma levels of pamrevlumab than patients without ascites. This may be because ascites fluid contains significant amounts of CTGF (data on file), and therefore may act as a sink for administered antibody. Patients with ascites that achieved high trough levels of pamrevlumab (>150 μ g/ml) had a median overall survival that was about 4 times longer than those that had lower trough levels (8.7 vs. 1.9 months). Together, these data suggest that it is important to achieve high plasma exposure to pamrevlumab in order to achieve maximal benefit.

In a phase 2 open label, study, randomized study in locally advanced unresectable pancreatic cancer (LAPC), patients received 35 mg/kg on days 1, 7 and 14 and then after every two weeks for total of six month in combination with gemcitabine and paclitaxel vs. combination of gemcitabine and paclitaxel. No safety concerns were seen with this dosing regimen and a phase 3 study in LAPC is ongoing. In an open label study in patients age 12 and above with non-ambulatory Duchenne Muscular Dystrophy (DMD), pamrevlumab has been administered at 35 mg/kg, every 2 weeks, for nearly two years with no safety concerns identified. A phase 3 study in LAPC is ongoing, and a phase 3 in non-ambulatory DMD is starting in the second quarter of 2020. Considered together, the data suggest that three weekly doses of pamrevlumab at 35 mg/kg, followed by bi-weekly administration for several more months should be well tolerated.

Supporting the dosing regimen of 30 mg/kg, dosed weekly until day 14, followed by every 2 weeks for the remaining treatment period, are data from the PRAISE clinical trial. PRAISE was a phase 2 placebo-controlled study in IPF with administration of pamrevlumab once every three weeks at 30 mg/kg, for 48 weeks. In PRAISE, the rate of FVC loss in the pamrevlumab-treated group was indistinguishable from that of placebo for the first 12 weeks, after which the rate of loss in the pamrevlumab-treated subjects was significantly slower (Richeldi et al. 2019). This observation suggests that adequate exposure to pamrevlumab to manifest its activity in IPF patients was not

achieved until about the 4th or 5th dose when it was administered at 30 mg/kg every 3 weeks. Repeat dose pharmacokinetic (PK) data in non-human primates indicates that achievement of steady-state levels of circulating pamrevlumab requires multiples doses, and that this is achieved faster at higher and more frequent doses. Computer modeling of pamrevlumab PK in humans also suggests that addition of at least one "loading dose" will result in more rapid achievement of efficacious plasma levels. This is the reason for the proposed dosing regimen in this acute-care setting.

This protocol has been prepared based on these rationales to address the current medical emergency, given the extremely high number of patients affected by COVID-19. The objective of this study is to investigate a novel anti-CTGF therapeutic to reduce the number of patients requiring mechanical ventilation. This is intended to address the most urgent need to preserve access to intense care unit support and to potentially reduce mortality.

2. STUDY OBJECTIVES

2.1. Primary objective

The primary objective of this study is to assess the effect of pamrevlumab on relevant clinical parameters in COVID-19 patients requiring hospitalization.

2.2. Secondary objective

The secondary objective of this study is to evaluate the safety and tolerability profile of pamrevlumab in COVID-19 patients requiring hospitalization.

2.3. Exploratory objective

An exploratory objective of this study is to assess the long-term effect of pamrevlumab on lung fibrosis in patients with SARS-CoV-2 infection requiring hospitalization.

3. STUDY ENDPOINTS

3.1. Primary endpoint

Proportion of patients not on ventilatory support \leq 15 days.

and qualitative changes by an independent imaging group.

3.2. Futility testing

Futility testing will be performed when 23 pamrevlumab patients completed 14 days of treatment. For futility testing of Stage 1 of the study, a responder rate definition will be evaluated. Patients randomized to receive pamrevlumab are considered responders if the total number of days on mechanical ventilation is ≤15 days after first dose of pamrevlumab and the patient is alive. In addition, chest high-resolution CT (HRCT) scans obtained at baseline and day 14 will used as supportive analyses in the assessment of futility. Such analyses will be based on both quantitative

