4. STUDY DESIGN AND METHODS

4.1. Study design

This is a randomized, open-label, parallel-arm study to investigate the efficacy and safety of pamrevlumab in patients with documented SARS-CoV-2 infection. The study consists of screening, a treatment period, and a follow-up period.

The study will enroll patients who have been hospitalized and who are not currently on invasive mechanical ventilation. The treatment period is open ended, and patients will be randomized to treatment with pamrevlumab or standard of care in a 1:1 ratio according to a pre-generated randomization list. Pamrevlumab dosing, 30 mg/kg IV, will be administered at day 1, day 7 and day 14. Day 1 is defined as the day of randomization which must also include administration of the first dose of pamrevlumab for patients in the active treatment arm.

Based on Investigator's decision, treatment may be continued every 3 weeks after day 14, up to 11 weeks.

Since the treatment scheme of pamrevlumab for this study is more intense as compared to previous studies conducted in IPF patients, as a further safety measure the first 3 patients randomized to receive the experimental drug will be treated one at a time, leaving a 1-week observation period between them.

A follow-up by visit or phone call will be performed 8 and 12 weeks after the end of the last dose of treatment. The treatment period for an individual patient will not exceed 11 weeks. The end of the study is defined as last patient last follow-up visit/phone call.

The study design has a total sample size of approximately 68 patients and consists of two stages. At the end of Stage 1 (Stage 1 requires 23 patients on pamrevlumab treatment arm), analyses of efficacy and safety will take place with a potential to stop the study for futility or for efficacy. A data

review committee composed of experts in respiratory medicine and intensive care will be involved in study oversight and interpretation of the study results. In patients showing worsening of clinical condition, independently of the treatment arm, the Investigator is free to introduce any therapy considered necessary.

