4.6. Determination of sample size

This study's sample size is based on Simon's two-stage design (Simon, 1989) on the pamrevlumab arm. For futility testing of Stage 1 of the study, a responder rate definition will be evaluated. Patients randomized to receive pamrevlumab are considered responders if the total number of days on ventilation is \leq 15 days after first dose of pamrevlumab and the patient is alive.

Key assumptions for sample size calculation include the following: (1) type I error rate, α (one-sided): 0.05; (2) power: 90%; (3) response probability of standard of care: 40%; (4) response probability of standard of care + pamrevlumab: 65%.

The null hypothesis that the true response rate is 40% will be tested against a one-sided alternative. In Stage 1, 23 patients will be accrued in pamrevlumab arm. If there are 9 or fewer responses in

these 23 patients, the study may be stopped. Otherwise, 11 additional patients will be accrued for a total of 34 in pamrevlumab treatment group. The null hypothesis will be rejected if 18 or more responses are observed in 34 patients on the pamrevlumab arm. This design yields a type I error rate of 0.05 and power of 90% when the true response rate is 65%.

The study will enroll approximately 50 patients in Stage 1 who will be randomized in 1:1 fashion (pamrevlumab vs. standard of care).

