4.7. Statistical methods

For futility testing in Stage 1, a responder rate definition will be used. Patients randomized to receive pamrevlumab are considered responders if the total number of days on ventilation is \leq 15 days after the first dose of pamrevlumab. In addition, chest HRCT scans obtained at enrollment and day 14 \pm 2 will used as supportive analyses in the assessment of futility.

Analysis of continuous endpoints will be conducted using analysis of covariance (ANCOVA) model with baseline value as a covariate and relevant baseline prognostic factors as other covariates.

Analysis of categorical endpoints will be conducted using either Fishers Exact test or Cochran-Mantel-Haenszel test comparing the categories between the two treatment arms.

Analysis of the time to mechanical ventilation, time to all-cause mortality, and time to hospital discharge, respectively, will be undertaken by plotting Kaplan-Meier curves. Hazard ratios will be estimated using the Cox proportional hazards model and these will be presented together with 95% two-sided confidence intervals. Other statistical methods will be applied, as appropriate.

5. Subject withdrawal criteria

Subjects may withdraw from the study at any time, for any reason. Reasons for discontinuing study drug treatment, as well as reasons for withdrawing from study, will be captured on CRF.

Reasons for withdrawing the subject from the study may include the following:

- 5.1. Any safety concern in the Investigator's opinion, that precludes further study participation
- 5.2. Pregnancy
- 5.3. Withdrawal of Consent

6. Pamrevlumab: storage, preparation and use

Pamrevlumab is a fully human IgG1 kappa monoclonal antibody that binds to CTGF and is formulated as solution for administration by IV infusion.

Pamrevlumab is supplied in single-use glass vials containing sterile, preservative-free solution 10 mg/ml pamrevlumab. The solution is composed of 10 mg/mL pamrevlumab, 1.60 mg/mL L-histidine, 3.08 mg/mL L-histidine HCl, 8.01 mg/mL sodium chloride, and 0.05 mg/mL polysorbate 20, resulting in a solution with a tonicity of approximately 290 mmol/kg and a pH of 6.0.

Vials of pamrevlumab must be stored refrigerated (2°C to 8°C), in a temperature- controlled and monitored environment, protected from light, and in a securely locked area to which access is limited to appropriate study personnel. Documentation of the storage conditions must be maintained.

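### Sections 3.2 and 4.6 name different sets of 23 patients for the Stage 1 look (completed versus accrued), so early deaths and stoppers may be left out of the futility count

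*Protocol*

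**What the plan says.** Four places in the protocol bear on who is counted at the Stage 1 look.

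- Section 3.2 (Futility testing) sets the timing: "Futility testing will be performed when 23 pamrevlumab patients completed 14 days of treatment".
- Section 3.2 then defines response: "Patients randomized to receive pamrevlumab are considered responders if the total number of days on mechanical ventilation is ≤15 days after first dose of pamrevlumab". The sentence adds a survival condition: "after first dose of pamrevlumab and the patient is alive". The definition is therefore written for randomized patients, and a death is a non-response.
- Section 4.6 (Determination of sample size) sets the rule: "In Stage 1, 23 patients will be accrued in pamrevlumab arm". The study may be stopped if those 23 yield 9 or fewer responses. Otherwise 11 more are accrued, for 34 in total.
- Section 4.1 (Study design) is neutral between the two: "Stage 1 requires 23 patients on pamrevlumab treatment arm".

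On overall numbers, section 4.6 says "The study will enroll approximately 50 patients in Stage 1 who will be randomized in 1:1 fashion", which is about 25 per arm. Sections 4.1 and 4.2 give a total of about 68.

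The protocol foresees exits before Day 14. Section 4.5 withdraws patients who are given certain listed therapies, including as rescue for worsening. Section 5 allows withdrawal for safety or of consent. Section 6 ends treatment after a hypersensitivity reaction. No section says how such patients count at the look.

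**The concern.** The number 23 does two jobs: it triggers the look in 3.2 and it is the denominator of the boundary in 4.6. Suppose two pamrevlumab patients have died by the time 23 have completed 14 days. Then 25 have been dosed, and the protocol has no boundary for 25. A team holding a 9-of-23 rule could easily apply it to the 23 who triggered the look.

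That set is selected on something close to the outcome. A patient must survive and stay on treatment to Day 14 to belong to it, so the survival condition in the responder definition does no work before that day. Withdrawal for rescue after worsening is also related to outcome.

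The 40% and 65% rates in 4.6 are given for the treatments, with no restriction to completers. If the boundary is used in a completer subset, its operating characteristics are not the planned ones. An ineffective drug could then pass Stage 1 more often than the design intends.

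**Working it through.** **Inputs from section 4.6.** Null rate 40%, alternative 65%, power 90%, "type I error rate, α (one-sided): 0.05". Stage 1 has 23 patients and stops at 9 or fewer responses. The final count is 34, and the null is rejected at 18 or more.

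**Input not in the protocol.** The share d of dosed pamrevlumab patients who do not complete 14 days is an assumption, shown over a range.

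**Step 1: the plan's own figures.** Exact two-stage binomial: sum over x = 10 to 23 of P(X₁ = x | 23, p) × P(X₂ ≥ r − x | 11, p), where r is the final cut-off.

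- With r = 18, type I error is 0.086 and power is 0.947. The stated 0.05 and 90% do not reproduce.
- With r = 19, type I error is 0.044 and power is 0.900.
- A search of two-stage designs returns 23 and 34, with the Stage 1 limit of 9, as the minimax design that rejects on more than 18 responses.

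The sizes and the Stage 1 limit are therefore sound. The final cut-off is a separate matter and does not affect the Stage 1 figures below.

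**Step 2: the Stage 1 rule on all 23 accrued patients.** P(X ≤ 9 | 23, 0.40) = 55.6%, so an ineffective drug passes 44.4% of the time. At 65% it passes 99.0% of the time.

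**Step 3: the same rule on 23 completers, all lost patients non-responders.** The completer rate is 0.40/(1 − d).

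| d lost | completer rate | chance of stopping | chance of passing |
|---|---|---|---|
| 0% | 0.400 | 55.6% | 44.4% |
| 5% | 0.421 | 47.4% | 52.6% |
| 8% (2 of 25) | 0.435 | 42.1% | 57.9% |
| 10% | 0.444 | 38.4% | 61.6% |
| 15% | 0.471 | 29.2% | 70.8% |
| 20% | 0.500 | 20.2% | 79.8% |

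If the final 34 were also completers, false rejection under the written cut-off of 18 would rise from 8.6% at d = 0 to 20.2% at d = 10%.

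**Step 4: the opposite case.** If the 10% lost are all responders who recovered and left, the completer rate is (0.40 − 0.10)/0.90 = 0.333. The chance of stopping is then 79%, higher than planned.

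**Step 5: where the sign changes.** Let f be the non-responder share among those lost. The completer rate is (0.40 − d(1 − f))/(1 − d). Setting this to 0.40 gives d(1 − f) = 0.40d, so f = 0.60. Above 60% non-responders among those lost, the rule is too easy to pass; below 60%, it is too hard.

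**Step 6: the timing.** After 14 days of follow-up nobody can have more than 14 ventilation days, so a limit of 15 cannot be exceeded. At such a look, response reduces to being alive. Any redefinition of the set therefore also needs an assessment day.

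**The case against.** A reader might infer from 3.2 that early deaths and stoppers never enter the responder denominator. The protocol does not say that. The sentence states when the look happens, not who is counted. The definition that follows covers randomized patients and fails those who die, and 4.6 puts the boundary on accrued patients. This stands: exclusion is a possible reading, not a stated rule.

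The numbers do not settle the reading. About 25 per arm in Stage 1 would fit 23 completers plus two lost, but it could also be 46 rounded up. The total of about 68 is exactly 2 × 34, which leaves no room to replace non-completers and favours the accrued reading.

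The direction of bias is not fixed either, as step 4 shows. The protocol does not say whether a patient discharged early has completed 14 days.

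A reader might also infer that the look loses its protective function. That goes too far. The rule is non-binding, since the study may (not must) be stopped. Section 4.1 plans efficacy and safety analyses at Stage 1 with a data review committee, and section 7 foresees a safety monitoring board, so early deaths could be seen there. Stopping drug also need not mean losing the outcome, because section 5 separates it from leaving the study.

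Finally, the counting of withdrawals at an interim look is often left to the analysis plan. That would answer a mere gap. It does not answer two protocol sections that attach the same number to different sets.

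**Conclusion.** The point holds as a conflict to be reconciled, of moderate severity. Sections 3.2 and 4.6 attach the number 23 to patients who completed and to patients who were accrued, and the boundary exists only for 23. Applying it to the completers who trigger the look would select on outcome, contrary to the responder definition.

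The size depends on two assumptions that the protocol does not supply: how many are lost before Day 14, and how they fared. If all are non-responders, the chance of stopping an ineffective drug falls from 56% to between 47% and 20% for losses of 5% to 20%. If most are recovered patients, it rises instead. Exclusion of early deaths as a settled rule, and a futility look without any protective value, both go beyond what the protocol supports.

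**What to change.** In 3.2 and 4.6, use one definition:

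- **Set.** The Stage 1 set is the first 23, and the final set the first 34, patients randomized to pamrevlumab who received the first dose, whether or not they complete treatment.
- **Timing.** Hold the look once each of the 23 has reached a single stated assessment day, died or left the study. That day must leave enough follow-up from first dose for more than 15 ventilation days to be possible, so 14 days is too short.
- **Counting.** Death or unknown status by that day is non-response. A patient who stops drug but has known status is classified by actual outcome, not scored as a failure for stopping.
- **Consistency.** Section 4.7 restates the responder definition ("For futility testing in Stage 1, a responder rate definition will be used") without the survival condition. Align it with 3.2 and 4.6.

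The cost is a few sentences, a slightly later look and a possibly lower observed responder rate. No extra patients are needed. In the schedule of events, the oxygen and ventilation row runs only to Day 14, so ventilation status would have to be recorded up to the chosen day.

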3.3. Secondary endpoints

3.3.1. PaO_2/FiO_2 ratio as categorical variable: mild 200 mmHg < $PaO_2/FiO_2 \le 300$ mmHg; moderate 100 mmHg < $PaO_2/FiO_2 \le 200$ mmHg; severe $PaO_2/FiO_2 \le 100$ mmHg.

- 3.3.2. For patients already on mechanical ventilator at time of randomization, the number of days on ventilator after randomization.
- 3.3.3. For patients not on mechanical ventilator at time of randomization, the number of days not requiring invasive mechanical ventilation (i.e., ventilator-free days).
- 3.3.4. PaO_2/FiO_2 ratio as continuous variable.
- 3.3.5. Resting SpO₂ adjusted by FiO₂.
- 3.3.6. Change in oxygen supplementation requirements.
- 3.3.7. Quantitative and qualitative assessment of pulmonary lesions by chest HRCT scans at baseline and at day 14 and week 12.
- 3.3.8. Time to hospital discharge.
- 3.3.9. Time to all-cause mortality up to 28 days.
- 3.3.10. Proportion of patients discharged from ICU and alive within 28 days.
- 3.3.11. Proportion of patients alive within 28 days.

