4.3. Diagnosis and main criteria for inclusion

Eligible patients are those with documented COVID-19, age \geq 18 to \leq 80 years with interstitial pneumonia (findings of consolidation or ground glass opacities as assessed by chest HRCT) and respiratory distress, defined as PaO₂/FiO₂ ratio of \geq 100 \leq 300 mmHg, requiring supplemental oxygen and hospitalization.

Exclusion criteria for the study are the following:

- Invasive mechanical ventilation at screening;
- Pregnancy;
- Incapacity to express a valid informed consent;
- Known hypersensitivity to monoclonal antibodies used as experimental drugs for any clinical indication.

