9. SCHEDULE OF EVENTS

ASSESSMENTS	Screening		Treatment											ONLY If EOT = Day 14 ^{2,4}	ONLY If EOT = Day 14 ^{2,4}	Continued Treatment visits for eligible subjects (CTV)	Follow-up			
	Up to 72 hrs prior to Day 1	Day 1 (ba seli ne)	Day 2	Day 3	Day 4	Day 5	Day 6	Day 7	Day 8	Day 9	Day 10	Day 11	Day 12	Day 13	Day 14 ⁴	Day 21 (+/- 2 days)	Day 28 (+/- 4 days)	Dosing Q 3 wks +/- 2 days: Week 5, 8,	Week 12 for all subjects	4 weeks (+/- 7 Days) after last Pamrevlu mab dose
Informed consent	Х																			
Eligibility criteria	Х																			
Medical History	Х																			
Demographic information	Х																			
Physical examination	Х																			
Vital signs ³	Х	X1	Х	Х	Х	Х	Х	X ¹	Х	Х	Х	Х	Х	Х	X ¹			X ¹		
ECG	Х																			
Chest HRCT	Х														Х				Х	
Laboratory assessments (local)	Х	Х	Х	Х	Х	Х	Х	Х	Х	Х	Х	Х	Х	Х	Х			Х		
Blood samples for Immunogenicity Assessments		Х						Х							Х					Х
Urine pregnancy test ⁶	Х																			
Randomization		Х																		
Concomitant medications	Х	Х	Х	Х	Х	Х	Х	Х	Х	Х	Х	Х	Х	Х	Χ	Х	Х	X	Х	Х
Infusion		Х						Х							Х					
Arterial Blood Gases (ABG) ³	Х	Х	Х	Х	Х	Х	Х	Х	Х	Х	Х	Х	Х	Х	Х					
PaO ₂ /FiO ₂ ³	Х	Х	Х	Х	Х	Х	Х	Х	Х	Х	Х	Х	Х	Х	Χ					
Resting SpO ₂ (3 times/day) ³	Х	Х	Х	Х	Х	Х	Х	Х	Х	Х	Х	Х	Х	Х	Х					
Oxygen supplementation Needs ^{3, 5}	Х	Х	Х	Х	Х	Х	Х	Х	Х	Х	Х	Х	Х	Х	Х					
Adverse events	Х	Х	Х	Х	Х	Х	Х	Х	Х	Х	Х	Х	Х	Х	Х	Х	Х	Х	Х	Х
Survival and Hospital Discharge Status																Х	Х		Х	Х

¹On infusion days, vitals taken within 30 minutes prior and 30 min after infusion; otherwise vitals taken daily ²Follow-up visits to be done in person or by phone ³Only measured until subject is discharged from the ICU/CCU. ⁴Subjects ending treatment on Day 14 should be contact by phone or return for a visit on Days 21 and 28 for a vital status check. ⁵Including need for mechanical ventilation including ventilator settings, or supplemental oxygen including mode of oxygen delivery ⁵Only for women of childbearing potential or last menstruation <1 year.

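### Three secondary-endpoint rules handle improving patients badly: no PaO2/FiO2 category above 300 mmHg, oxygenation records that end at ICU discharge, and an ICU endpoint that a never-ICU survivor cannot meet

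*Protocol*

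**What the plan says.** **The categorical oxygenation endpoint.** Protocol 3.3.1 defines the PaO2/FiO2 "ratio as categorical variable: mild 200 mmHg" up to 300 mmHg, then "moderate 100 mmHg <" up to 200, then severe at 100 or below. No category lies above 300. Endpoint 3.3.4 takes the same "ratio as continuous variable". Section 4.7 compares categorical endpoints between arms by Fisher's exact or the Cochran-Mantel-Haenszel (CMH) test.

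**Entry.** Section 4.3 asks for a PaO2/FiO2 "ratio of \geq 100 \leq 300 mmHg" in patients "requiring supplemental oxygen and hospitalization". Section 4.1 says: "The study will enroll patients who have been hospitalized and who are not currently on invasive mechanical ventilation". Neither section requires ICU admission.

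**Measurement.** The Schedule of Events (section 9) marks arterial blood gases, PaO2/FiO2, resting SpO2 and oxygen needs daily up to Day 14. All four rows carry footnote 3, which ends measurement when the subject leaves the ICU/CCU. By footnote 5, the oxygen-needs row also records mechanical ventilation.

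**The ICU endpoint.** Endpoint 3.3.10 is "Proportion of patients discharged from ICU and alive within 28 days". After Day 14 the schedule lists "Survival and Hospital Discharge Status" and does not name ICU status. Its Day 21 and Day 28 columns apply only to patients whose treatment ended on Day 14.

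**The concern.** Each rule works for a patient who stays ill and breaks down for one who gets better. The 3.3.1 scale describes patients at entry but cannot record recovery beyond its upper edge. Footnote 3 makes a missing oxygenation value a consequence of improvement, and leaving the ICU is a post-randomisation event that treatment may change. Endpoint 3.3.10 gives no credit for avoiding the ICU, although the rationale (section 1.6) names preserving access to intensive care as a purpose of the trial.

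If pamrevlumab speeds recovery, the later observed values in its arm over-represent the patients who have not recovered. If it keeps patients out of the ICU, 3.3.10 can move the wrong way. A statistical analysis plan can set handling rules, but it cannot recover values that the schedule never collected.

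**Working it through.** The protocol gives no figure to reproduce here, so the first two parts are checked by setting the provisions side by side. The third also has a short illustration.

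**1. Category gap (3.3.1 against 4.3).** Entry range: 100 to 300 mmHg. Category range: everything up to 300. The scale is open at the bottom (100 or below is severe) and closed at the top. A patient who enters at 250 and improves to 320 moves from mild to no category. The value itself is not lost: while it is measured, 3.3.4 uses it.

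**2. Stop in measurement (footnote 3 against 3.3.1 and 3.3.4 to 3.3.6).** On any day up to Day 14 there are three groups:
- Patients in the ICU/CCU: measured.
- Patients who entered and have left: not measured, and missing because they improved.
- Patients never in the ICU/CCU: no discharge occurs, so read literally they stay on the daily schedule to Day 14, and the footnote gives them no stopping point.

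The second group is the loss. If one arm leaves the ICU sooner, it loses more of its improved patients, and an observed-value comparison tilts against it. Ventilation status after ICU discharge falls under the same stop.

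**3. ICU endpoint (3.3.10 against 4.1 and 4.3).** The denominator is not stated. With all patients, a never-ICU survivor is a failure. With ICU patients only, that survivor is excluded and the comparison conditions on a post-randomisation event. Neither reading allows a success.

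Inputs for the illustration, all assumed because the protocol gives no ICU rates:
- f = share never in the ICU: 20%, 30% or 40% on control, paired with 40%, 50% or 65% on pamrevlumab.
- q = probability that an ICU patient is discharged from the ICU alive by Day 28: 50% or 70%, the same in both arms.
- All never-ICU patients are alive at Day 28.

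Formulas:
- As worded, all patients in the denominator: (1 − f) × q
- Never-ICU survivors counted: f + (1 − f) × q

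For f = 30% and 50% with q = 50%: as worded, 0.70 × 0.50 = 35.0% on control and 0.50 × 0.50 = 25.0% on pamrevlumab. With never-ICU survivors counted, 0.30 + 0.35 = 65.0% and 0.50 + 0.25 = 75.0%.

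| f control / pamrevlumab | q | As worded: control / pamrevlumab | Difference | Never-ICU survivors counted: control / pamrevlumab | Difference |
|---|---|---|---|---|---|
| 30% / 50% | 50% | 35.0% / 25.0% | −10.0 | 65.0% / 75.0% | +10.0 |
| 30% / 50% | 70% | 49.0% / 35.0% | −14.0 | 79.0% / 85.0% | +6.0 |
| 40% / 65% | 50% | 30.0% / 17.5% | −12.5 | 70.0% / 82.5% | +12.5 |
| 40% / 65% | 70% | 42.0% / 24.5% | −17.5 | 82.0% / 89.5% | +7.5 |
| 20% / 40% | 50% | 40.0% / 30.0% | −10.0 | 60.0% / 70.0% | +10.0 |
| 20% / 40% | 70% | 56.0% / 42.0% | −14.0 | 76.0% / 82.0% | +6.0 |

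Differences are pamrevlumab minus control, in percentage points. In general, with q equal in both arms, the difference as worded is −q times the difference in f, and the corrected difference is (1 − q) times it. The reversal of sign therefore follows from the wording whenever treatment raises f. Only its size depends on the assumed rates.

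**The case against.** The strongest reply is that the parts pull against each other. If many patients never enter the ICU, footnote 3 does not remove them. If footnote 3 presumes that everyone is in the ICU/CCU, 3.3.10 loses almost nobody. This stands as a limit on reach: the two problems affect different patients, and the mix is unknown. It does not remove either one, because no entry criterion settles the mix.

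Three stronger readings are tempting, and the text does not support them.
- A reader might infer that all later oxygenation values come from patients still in the ICU. Read literally, never-ICU patients stay on the daily schedule.
- A reader might infer that values above 300 are lost. They are recorded while measurement lasts and used in 3.3.4; only 3.3.1 has no place for them.
- A reader might infer that 3.3.10 drops never-ICU patients. With all patients in the denominator they are counted, but as failures.

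It can also be said that a top category is a handling rule for the analysis plan, and that deaths and good outcomes are credited elsewhere (3.3.3, 3.3.8, 3.3.9, 3.3.11). For deaths that is fair: a separate death category, or a particular ordinal model, is optional. But 3.3.1 sets its own cut-points in the protocol, and as written they leave out recovery. Credit in other endpoints does not repair 3.3.10.

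**Conclusion.** The point holds for secondary endpoints and should be corrected. Followed as written, 3.3.1 cannot classify recovery above 300 mmHg. Footnote 3 loses oxygenation and oxygen-need data after ICU discharge before Day 14, and leaves the stopping point for never-ICU patients undefined. Endpoint 3.3.10 can move against a treatment that prevents ICU admission.

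The size of the bias cannot be given from the protocol. The tabulated range (10 to 17.5 points against pamrevlumab as worded, 6 to 12.5 points in favour when never-ICU survivors count) shows direction only. It rests on assumed ICU rates, on equal q in both arms and on a treatment that does keep patients out of the ICU. A reader might want one count of patients lost to the oxygenation comparisons. None can be supported, because leaving the ICU and exceeding 300 affect different endpoints and neither rate is stated. If every patient is in the ICU/CCU in practice, the 3.3.10 problem has little effect and the footnote 3 problem applies to everyone. The category gap stands either way.

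**What to change.** 1. **3.3.1:** add a category above 300 mmHg, and treat the categories as ordered within the CMH test that section 4.7 already allows.
2. **Footnote 3:** record resting SpO2, FiO2 and oxygen mode, including ventilation status, on any ward until Day 14 or hospital discharge. State that 3.3.1 and 3.3.4 after ICU discharge are limited by unmeasured blood gases, so that 3.3.5 and 3.3.6 carry the comparison in all patients.
3. **3.3.10:** redefine as *alive and not in ICU at Day 28*, among all randomised patients. Add ICU status to the Day 28 status check, and make that check for all patients, including those who continue treatment after Day 14.

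Cost: changes to protocol and CRF wording, a few more routine bedside entries per patient, and one added status item at Day 28. No additional blood-gas sampling is needed.
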